The proposed study will help fill this alarming gap in the evidence base for adolescents with ADHD. The study is significant for several reasons. It will occur in existing behavioral health clinics to test front-line treatment effectiveness. Both protocols (CASH-AA and MIP) are evidence-based, affording a rigorous test of the best available treatment options for this clinical group. The test has immediate real-world implications: Families enrolled in specialty treatment settings invariably prefer behavioral services only, but they need to know whether integrated medication interventions can provide a meaningful boost to outcomes that are most important to them. Importantly, whereas ethnic minorities and also girls with are severely underserved and under-researched, the current study will focus on urban minority teens, and about half the sample will be female. Also, this study will be among the first to test evidence-based ADHD treatment options for adolescents who use substances, another significantly underserved and high-priority clinical risk group.

This comparative trial will randomly assign 140 adolescents with ADHD to Behavioral Only (containing CASH-AA) or Integrated (containing CASH-AA + MIP) treatment. The CASH-AA and MIP protocols will be incorporated in existing services in four clinics that support both study conditions. Adolescents and caregivers will complete research interviews at baseline and 3, 6, and 12-months follow-up. Multilevel modeling will compare conditions on symptom, quality of life, and service use outcomes and also test patient-centered heterogeneity of treatment effects and individual difference effects. Semi-structured interviews will document

family-specific rationale for decisions about initiating and continuing in behavioral and medication interventions, along with suggestions for improving the respective treatment services. The study has three specific aims:

Aim 1: Comparative Impact on Client Functioning

Hypothesis 1: Reduced Symptoms. Integrated clients will show greater decreases in ADHD symptoms (inattention, hyperactivity/impulsivity) and comorbid problems (conduct problems, drug use) than Behavioral Only clients.

Hypothesis 2: Improved Quality of Life. Integrated clients will show greater improvements in executive functioning (self-regulation, self-organization) and school functioning (grades, attendance, motivation) than Behavioral Only.

Aim 2: Comparative Impact on Service Utilization

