Hypothesis 3: Better Treatment Attendance. Integrated clients will attend more behavioral therapy sessions and medication management sessions than Behavioral Only clients.

Hypothesis 4: Greater Medication Acceptance and Treatment Satisfaction. Integrated clients will more often consent to medication, show greater medication compliance, and report greater overall satisfaction than Behavioral Only.

Aim 3: Examine Patient-Centered Outcomes

Research Question 1: Heterogeneity of Treatment Effects. Will clients with co-occurring substance use problems have worse treatment outcomes than those without? Will there be outcome differences based on age, ethnicity, sex?

Research Question 2: Analysis of Individual Differences. Across treatment conditions, will clients who choose to start a medication regimen have better treatment outcomes than those who do not?

Study Design

This study emphasizes ecological validity: Both protocols will be implemented in existing outpatient behavioral services by agency clinicians. To promote internal validity, randomization will occur within site at both the client and therapist level (i.e., study therapists at

each site will be randomly assigned to condition). The primary benefit of “doubly randomized” designs is that they minimize potential bias related to site effects—because randomization occurs within each site—and therapist sampling bias—because therapists are randomly assigned to condition. The use of a Behavioral Only condition will control treatment expectancy effects. Therapists will be trained and supervised to implement CASH-AA and MIP as part of their otherwise routine duties; that is, the protocols will be additional components of their usual practice for study cases. To maximize protocol exposure, and to promote consistency in the timing of protocol implementation across conditions and cases, therapists will be asked to implement CASH-AA and MIP at the start of treatment (unless contraindicated).

Note: (1) ADHD medication will be available to all Behavioral Only cases via routine site practices for ADHD treatment; and (2) MIP supports family decision-making about medication but does not require families to start a medication regimen.

Sample Description

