intensive family engagement and family-agency coordination efforts to help families overcome barriers to enrolling in services, procedures especially valuable for enrolling hard-to-engage families. Linking procedures will cease upon completion of the first intake interview (after which randomization will occur). After linking is completed, research staff will maintain contact with families solely to complete follow-up interviews, which will occur with every randomized family regardless of treatment attendance.

Randomization to study condition and therapist assignment. Cases will be randomly assigned to study condition after completing an intake interview at the assigned site. Urn randomization will promote balance between conditions on 3 variables: sex, ethnicity (Hispanic, African-American, Other), and ASU problems (Yes, No). Once randomized, cases will be assigned to a study therapist in alternate turns. Note that in some sites, it will be necessary to follow “nearly random” assignment to condition, if the given site assigns cases to clinicians based on a shared rotation of case assignment. That is: Any given case is assigned to the next available clinician in the duty rotation, or, the clinician who is on duty during the given intake appointment. Treatment site therapists who agree to participate as study therapists will be consented in their private offices by research staff. We anticipate some degree of therapist dropout due to staff turnover during two years of enrolling study cases. When a study therapist drops out in either condition, the given site will be asked to nominate two potential replacements, and the new therapist will be randomly selected from that pair. All partnering treatment sites will be in close proximity to assigned study participants and easily accessible via public transportation. Each site will routinely prescribe weekly treatment sessions and offer in-house psychiatric support for all cases. All therapists at each site who treat adolescent clients and who volunteer to participate will be accepted into the study randomization pool.

Study Conditions

Behavioral Only Condition: Changing Academic Support in the Home for Adolescents with ADHD (CASH-AA)

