Executive functioning will be measured with the *Behavior Rating Inventory of Executive Function*, a parent-report measure of behavior problems linked to executive functioning and commonly found in ADHD youth. It has been validated on ADHD outpatient samples and teens with mixed diagnoses. School functioning indicators will derive from three sources. Therapists will acquire school transcripts to document grades and attendance. The *CASI-A* will yield data on past-year academic, attendance, and behavior problems. The *Bonding to School (BTS)* is a self-report measure of adolescent bonding to teachers and orientation to school used with high-risk samples.

Service Utilization, Treatment Satisfaction, and Semi-Structured Post-treatment Interview

Research staff will ask study therapists to gather data from *Clinical Contact Logs* at each site on the total number of sessions attended by study clients and the type and amount of medications prescribed. The *Services Assessment for Children and Adolescents (SACA)* is a structured assessment of parents' reports of their children's behavioral health service utilization, perceived need for services, barriers to services receipt, and retrospective estimate of days of ADHD medication use. It has demonstrated strong agreement with administrative service records; test-retest reliability of lifetime and past year service use are also strong. The *Client Satisfaction Questionnaire (CSQ)* measures consumer satisfaction with the quality and effectiveness of treatment services and will be completed by adolescents and caregivers. Internal consistency ranges are high, and concurrent validity is supported by strong correlations with therapist and client improvement ratings. Study therapists will collect weekly medication use logs during each session via caregiver and/or teen report: type and dose of current prescription, and number of days that medication was taken since last log entry. This will yield interval-level prospective data, the most rigorous self-report method for medication use. *Semi-structured qualitative interviews* will be administered to teens and caregivers at 12-month FU to capture judgments about treatment acceptability and effectiveness of intervention components as well as family-specific rationale for medication decisions.

Therapist Measures

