Based on 20 years of experience engaging high-risk adolescents and their families into longitudinal research, we expect to have rates of missing assessment data on outcome variables between 10-15%. All proposed analyses involving client outcome data will be carried out in Mplus, which provides full information maximum likelihood estimation (MLE), which produces unbiased parameter estimates under the assumption that data are missing at random. Moreover,

MLE outperforms other missing data approaches, such as listwise deletion, even when MAR is not met.

Risks And Benefits

Potential Study Risks

Potential Risks for Client Participants: Research Interviews and Treatment Session Recording

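### School transcripts for grades and attendance are collected by treating therapists, with no stated procedure for clients who leave treatment, so missing records may be related to attendance and possibly to arm

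*Combined protocol and SAP*

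**What the plan says.** All references are to the combined protocol and SAP.

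- **Outcome.** Hypothesis 2 (Aim 1) expects Integrated clients to improve more in "school functioning (grades, attendance, motivation) than Behavioral Only". The Aims 1 & 3 analysis is an intent-to-treat growth model over four time points.
- **Source.** Under Quality of Life Indicators, "School functioning indicators will derive from three sources": transcripts, the CASI-A and the Bonding to School scale. For the first, "Therapists will acquire school transcripts to document grades and attendance". The CASI-A "will yield data on past-year academic, attendance, and behavior problems".
- **Follow-up.** Under Linking to treatment, after linking is complete "research staff will maintain contact with families solely to complete follow-up interviews, which will occur with every randomized family regardless of treatment attendance".
- **Attendance.** Hypothesis 3 (Aim 2) states that "Integrated clients will attend more behavioral therapy sessions and medication management sessions than Behavioral Only clients".
- **Missing data.** Citing long experience of engaging families in longitudinal research, the plan says "we expect to have rates of missing assessment data on outcome variables between 10-15" per cent. It relies on full information maximum likelihood under missing at random (MAR).
- **Attrition check.** Under Preliminary Analyses and Refuser Analyses, a logistic regression examines failure to contact clients at follow-up.

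**The concern.** Two data streams feed the same intent-to-treat analysis but rest on different contacts. Interviews depend on research staff, who pursue every randomized family. Transcripts depend on the therapist, whose link to the family is treatment itself. Clients are randomized after the intake interview and assigned a therapist only afterwards, so a family that never comes back is in the analysis set but may never meet the person who is to obtain its transcript. Follow-up runs to 12 months from baseline, and a case may close well before that. Expected therapist turnover is a further route to loss.

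If transcripts are obtained less often for clients who attend little, and attendance differs by arm, the transcript comparison shifts toward clients retained in care. Retention is a post-randomization result. Any school benefit that arises from keeping clients in treatment would then be partly hidden, and fewer records would be available than the missing-data section suggests.

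**Working it through.** **Does any stated provision close the gap?**

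1. *Follow-up guarantee.* It is worded for interviews. No section extends it to school records.
2. *Therapist duties.* Therapist Measures lists four kinds of data, and transcripts are not among them. They are also absent from the chart-data list under Potential Risks for Therapist Participants and from both reimbursement lists. Timing and school periods are not given anywhere.
3. *Attrition check.* It models failure to contact. A family that was interviewed but has no transcript counts as followed.
4. *Expected missingness.* The 10–15% figure rests on engaging families in research, not on record retrieval by clinicians.
5. *Growth model.* The listed terms are condition, baseline substance use, sex, age, ethnicity, family income, caregiver education and site. Session attendance is not listed, so missingness that depends on attendance is MAR only so far as these terms and the observed outcomes account for it.

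**How large could the effect be?** The plan gives no dropout rate, transcript completion rate, effect size or power calculation, so there is no figure of its own to reproduce. From the plan: 140 randomized, or 70 per arm if split equally. The following are assumptions:

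- therapy dropout d of 30% in Behavioral Only and 15% in Integrated;
- dropouts 0.5 SD worse on the school outcome in both arms, with no other arm effect;
- transcripts for 85% of retained clients, and for a fraction r of dropouts, with r = 20% or 50%.

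Formulas, per arm:

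- proportion observed: o = 0.85(1 − d) + r·d
- share of dropouts among those observed: s = r·d / o
- true difference: 0.5 × (0.30 − 0.15) = 0.075 SD
- observed difference: 0.5 × (s in Behavioral Only − s in Integrated)

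*r = 20%*
- Behavioral Only: o = 0.595 + 0.060 = 0.655 (34.5% missing); s = 0.060/0.655 = 0.092.
- Integrated: o = 0.7225 + 0.030 = 0.7525 (24.8% missing); s = 0.030/0.7525 = 0.040.
- Observed difference 0.5 × (0.092 − 0.040) = 0.026 SD; bias 0.026 − 0.075 = −0.049 SD.

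*r = 50%*
- Behavioral Only: o = 0.595 + 0.150 = 0.745 (25.5% missing); s = 0.201.
- Integrated: o = 0.7225 + 0.075 = 0.7975 (20.3% missing); s = 0.094.
- Observed difference 0.054 SD; bias −0.021 SD.

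*Equal dropout, equal deficits.* The shares s match and the bias is zero. Missingness is still 25.5–34.5% if dropout is 30% in both arms, or 20.3–24.8% if it is 15% in both.

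*Equal dropout, unequal deficits.* If transcripts exist only for retained clients, bias = d × deficit in Integrated − d × deficit in Behavioral Only. With 30% dropout in both arms and deficits of 0.2 and 0.5 SD, this is 0.06 − 0.15 = −0.09 SD. Reversing the deficits reverses the sign.

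**Precision.** For a simple two-group comparison with assumed two-sided alpha 0.05 and 80% power, the detectable difference is (1.96 + 0.84) × √(1/n₁ + 1/n₂).

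| Transcripts available | Detectable difference (SD) |
|---|---|
| 70 and 70 (complete) | 0.474 |
| 63 and 63, or 59.5 and 59.5 (10% or 15% missing) | 0.499 or 0.514 |
| 52.2 and 55.8 (30%/15% dropout, r = 50%) | 0.540 |
| 45.9 and 52.7 (30%/15% dropout, r = 20%) | 0.566 |

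The standard error with complete data is √(2/70) = 0.169 SD, so a bias of 0.049 SD is about 0.29 of one standard error.

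**The case against.** Much of the case on the other side stands.

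- A reader might infer that transcripts will be missing mainly for clients who drop out. The plan does not say so. School records can be requested after therapy ends, and therapists have some duties at or after closure: a termination summary and paid post-treatment logs. What the documents show is an unspecified procedure; a link to attendance is likely but not stated.
- A reader might infer that the trial predicts different dropout by arm. Hypothesis 3 predicts more sessions attended, gives no magnitude, and could be true with equal dropout.
- The CASI-A gives a second, interview-based source for academic and attendance problems that does not depend on the therapist. This limits the exposure. It is not a full substitute: it records problems, not grades, and a past-year window at the 3- or 6-month interview would reach back about nine or six months before baseline.
- Both arms receive CASH-AA, including its school-contact module, so uneven delivery does not by itself create an arm difference. An unmasked therapist does not alter grades that the school records.
- The calculation compares observed cases at one time point. A four-wave likelihood model can recover part of the bias where earlier outcomes predict later ones, so it would be wrong to say that the planned estimation cannot help.
- Consent pages are not in the available text, so a school-record release may already exist.

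None of this supplies a procedure for clients who leave treatment, or a check on transcript completeness.

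**Conclusion.** The point holds as a weakness in how one outcome is collected. Therapists are the only named route to transcripts, the all-randomized guarantee stops at interviews, and the attrition check would not reveal missing transcripts. Missingness is likely to be related to attendance and may be related to arm; likelihood estimation under MAR may repair this only in part.

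The size is unknown because every rate used above is assumed. In the main scenarios the observed-case bias is about 0.02–0.05 SD against Integrated, with roughly 20–34% of transcripts missing per arm against an expected 10–15%. The bias vanishes with equal dropout and equal deficits, leaving a loss of precision, and it can change sign if deficits differ by arm.

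A reader might infer that most of any school benefit would be lost, since 0.049 of 0.075 SD is about 65%. That percentage describes a component created by the assumed dropout gap and deficit, so the documents do not support it as a statement about this trial. Confidence in the point is moderate. It merits correction because the remedy is cheap and missing records are harder to repair at analysis.

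**What to change.** - Obtain a school-record release from caregiver and adolescent at the existing follow-up-study consent, if it is not already included.
- Have research staff, not therapists, request transcripts or report cards for every randomized adolescent, for the same marking periods in both arms, regardless of therapy attendance.
- Report transcript completeness by arm and time point, and add a sensitivity analysis to the MAR assumption for the transcript outcomes.

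The cost is one form at a visit already taking place and a modest clerical load for research staff, who make repeated requests for up to 140 adolescents. The sentence limiting staff contact after linking to follow-up interviews would need a small amendment to allow record requests.

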This parametric comparative trial will randomly assign 140 inner-city adolescents with ADHD to (1) CASH-AA Only or (2) CASH-AA + MIP. Treatment will occur in community behavioral health clinics. All participants will receive behavioral interventions (CASH-AA): family psychoeducation in ADHD symptoms, executive functioning, and developmental impacts; family-based motivation and ADHD accommodation interventions; and academic training focused on home environment support and organizational skills. Half of the participants

will also receive medication decision-making interventions (MIP): ADHD medication psychoeducation, family decision-making interventions, and (for those who elect to start medication) coordinated medication management. Half of the sample will have comorbid substance use problems. Treatment will occur in three community clinics; therapists will be randomly assigned to study condition. Caregivers and adolescents will complete assessments at baseline, 3, 6, and 12-month follow-up. Multilevel modeling will compare the effectiveness of each condition on key patient and service use outcomes. Patient-centered analyses will explore differential treatment effects based on (a) Medication decision (yes/no); (b) Substance use comorbidity (yes/no); (c) Race/Ethnicity (Hispanic, African American).

Quantitative outcome analyses will test for service use effects, symptom reduction, and quality of life improvements that are primary reasons for seeking clinical services. Qualitative interviews will document family-specific rationale for decisions about medication, compliance with behavioral and medication interventions, and suggestions for improving services and service integration. Note that families assigned to CASH-AA Only will retain the option of pursuing ADHD medication through treatment-as-usual procedures at their respective clinic. Similarly, families assigned to CASH-AA + MIP will not be required to start ADHD medication. Instead, they will receive informed-choice interventions and can choose when and if to start medication; the study will assess the impact of these decisions on clinical outcomes.

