Study therapists will be asked to provide four kinds of study data: (1) Upon consenting to participate in the study, therapists will complete one questionnaire documenting their demographic characteristics and clinical training background, and a second questionnaire documenting their clinical strengths and preferred clinical practices. (2) When treating study cases, therapists will complete and submit the CASH-AA fidelity checklist and, for those in the Integrated condition, the MIP fidelity checklist after every session; and each condition will complete a brief checklist of evidence-based practices for adolescent behavior problems; all checklists (total completion time: 5 minutes) will be collected by research staff on a regular basis. (3) When treating study cases, therapists will audiorecord every session with consenting clients and submit the recordings to research staff on a regular basis. (4) Upon closing a study case, therapists will complete a termination summary of clinical activity that documents information about sessions held, participants in sessions, and treatment procedures that were the main foci of session activity.

Data Analysis

Preliminary Analyses and Refuser Analyses

All analyses will be preceded by examining distributional properties of variables, outliers, and need for using transformed variables or non-parametric tests. We will examine whether randomization successfully created equivalent study groups by conducting *t*-tests or chi-square tests on demographics and other variables; those that differ between groups will be entered as covariates in subsequent analyses. Logistic regression will examine potential biases due to failure to contact clients at follow-up on baseline characteristics, study condition, and their interactions. These analyses will determine whether the followed sample differs from the randomized sample and whether there is differential attrition by condition. Also, analyses on refuser characteristics will be conducted to inform the generalizability of the sample, as follows. Families completing the phone eligibility screening instrument will provide information on personal and family demographics. Families of eligible adolescents who refuse to participate in the baseline interview, or who participate in the baseline interview but do not complete an intake appointment at the assigned treatment site, will be asked to complete a brief study refuser

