LGC will proceed using Mplus version 7, as follows. First, we will test a series of growth curve models for each outcome, representing three forms of growth (no change, linear change, quadratic change), to determine the overall shape of the individual change trajectories; overall model fit will be evaluated by examining the chi-square, RMSEA, CFI, and TLI indices. Second, we will test unconditional models for all outcomes to obtain the average effect for change over time in outcome, without including treatment condition or other covariates. Third, we will add the two predictors, Condition (Behavioral Only vs. Integrated) and baseline Substance Use (SU+ vs. SU-) to the models in order to test the impact of each predictor on initial status and change over time. We will also test Condition X SU interactions, and if any are significant for a given outcome, we will re-run that model separately for the SU+ and SU- participants to test simple effects. Treatment effects (Aim 1) for any given outcome will be shown by a statistically significant effect parameter, as tested by the pseudo z test—calculated by dividing the coefficient by its standard error—associated with Condition. Heterogeneity of Treatment Effects (HTE; Aim 3) for any given outcome will be identified by a significant effect for the Condition X SU interaction term; post-hoc analyses will be used to explore these interactions to determine whether Integrated effects appeared to be stronger or weaker in SU+ versus SU- cases. Initially, all models will be adjusted for nuisance covariates: sex, age, and ethnicity; family income; caregiver education level; and treatment site. We will then further explore HTE (Research Question 1) by testing for outcome differences based on age, ethnicity, and sex subgroups. Per above we will use the sandwich estimator to control for therapist nesting. Effect size estimates for significant findings in Aims 1 and 3 analyses will be calculated based on Feingold's procedures for calculating effect sizes for LGC analyses. Also, for any outcome that deviates substantially from normality—typical for delinquency and SU data—we will use two-part growth curve models, which allow for the simultaneous estimation of separate but correlated continuous and categorical LGC models. Two-part models are used when a large number of participants report the absence of the given variable (i.e., no delinquent activities or SU), resulting in highly skewed data. In two-part models, the original distribution of the outcome is separated into categorical and continuous parts, each modeled by separate but correlated growth functions. In the categorical part, a binary indicator variable is created to indicate any vs. none of the outcome in question. The continuous part models the frequency of occurrence of the outcome given any positive occurrence.

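### Outside the fixed covariate list, adjustment depends on a baseline significance test, so sizeable imbalances in prognostic variables can go unadjusted, chiefly in the Aim 2 models

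*Combined protocol and SAP*

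**What the plan says.** The combined protocol and SAP has two covariate rules, and they stack.

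- **Data-driven rule** (Data Analysis, Preliminary Analyses and Refuser Analyses). The arms are compared by t-tests or chi-square "tests on demographics and other variables", and "those that differ between groups will be entered as covariates in subsequent analyses". The set of variables is open. No significance level is given, and nothing requires a variable to be related to the outcome.
- **Fixed rule** (Plan of Analysis for Main Outcomes: Aims 1 & 3). Here "all models will be adjusted for nuisance covariates: sex, age, and ethnicity; family income; caregiver education level; and treatment site". Baseline substance use also enters these growth models as a predictor. The Aim 2 plan takes over the same nuisance covariates, but it does not name substance use.

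Two features of the design bear on this. Urn randomization balances sex, ethnicity and substance use. Some sites, however, may depart from strict randomization "if the given site assigns cases to clinicians based on a shared rotation of case assignment" (Randomization to study condition and therapist assignment).

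**The concern.** A baseline test measures how far the arms differ relative to sampling error. It does not measure whether the variable predicts the outcome, which is what makes adjustment worthwhile. A rule built on it lets in weak predictors that happen to differ and leaves out strong predictors with a moderate difference.

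The variables left to this rule include plausible predictors. Sample Description projects conduct disorder at 53%, mood disorder at 42%, a childhood ADHD diagnosis at 33% and ADHD medication in childhood at 20%. None is on the fixed list.

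Aim 2 is the most exposed. Attendance, medication acceptance and satisfaction are each measured once, so no growth-curve intercept carries baseline status. Substance use, an urn factor, is missing from those models. So are baseline ADHD severity and earlier ADHD medication, which plausibly bears on acceptance.

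Because the tested set is open, the final model is also unknown until someone has seen the data and chosen what to test.

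**Working it through.** The documents give no significance level, power or sample-size calculation, so there is no figure of the plan's own to reproduce.

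**Inputs**
- Sample size: the study "will randomly assign 140 inner-city adolescents with ADHD" (Project Abstract), and "Half of the participants" also receive the medication protocol, so n = 70 per arm.
- Significance level: not stated. The plan says only that an effect "will be shown by a statistically significant effect parameter". Two-sided 0.05 is assumed; 0.10 is shown as a range.
- Projected rates of 20%, 33%, 42% and 53%: Sample Description.
- Correlation r between covariate and outcome: assumed, 0.3 to 0.5.

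**1. Largest imbalance the rule ignores**
- Continuous variable: 1.96 × √(2/70) = 0.331 SD. At level 0.10: 0.278 SD.
- Rate p: 1.96 × √(2p(1−p)/70).

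| p | Threshold (percentage points) |
|---|---|
| 20% | 13.3 |
| 33% | 15.6 |
| 42% | 16.4 |
| 53% | 16.5 |

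Example: earlier medication in 10/70 against 18/70 is an 11.4-point difference at a pooled rate of 20%. That is below 13.3 points, so it would not be adjusted.

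**2. How often this arises**
- Under simple randomization, the chance of an absolute difference above 0.20 SD is 23.7%. Subtracting the 5% that are flagged leaves about 19% per variable.
- A systematic difference of 0.2 SD would be flagged 22% of the time, and one of 0.3 SD 43% of the time.

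**3. Shift in an unadjusted comparison of outcome level** (imbalance × r)

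| Imbalance | r = 0.3 | r = 0.5 |
|---|---|---|
| 0.20 SD | 0.06 SD | 0.10 SD |
| 0.331 SD | 0.10 SD | 0.17 SD |

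This fits Aim 2 outcomes analysed as continuous. For medication acceptance, if analysed as yes/no, it is only a guide.

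**4. Behaviour of the rule.** Simulation of 40,000 trials with 70 per arm, one covariate, simple randomization and no clustering. Power is for an assumed true effect of 0.5 SD.

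| | r = 0.3 | r = 0.5 | r = 0.7 |
|---|---|---|---|
| Type I error, rule | 4.7% | 4.2% | 3.7% |
| Type I error, rule, given an unflagged imbalance above 0.2 SD | 6.2% | 8.3% | 10.5% |
| Power, rule | 83.8% | 84.8% | 85.7% |
| Power, always adjusting | 86.5% | 92.4% | 98.4% |

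Always adjusting gives an overall type I error of 4.9–5.0%. In the trials with an unflagged imbalance it gives 4.8–5.3%.

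**5. Chance entries.** With k independent tests at 0.05, the chance that at least one variable enters is 1 − 0.95^k: 40% for k = 10 and 64% for k = 20. The plan gives no k.

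**The case against.** The strongest reply is that most of the adjustment is already fixed. Six covariates are in every model whatever the tests show, substance use is always in the growth models, and three variables are urn-balanced. This stands. A reader might infer that the baseline tests govern adjustment as a whole; the Aims 1 & 3 and Aim 2 sections show that they do not.

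Three other strong readings also fail.

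- **That the rule inflates false positives.** Overall it does not: simulated type I error is 3.7–4.7%. The excess appears only in trials with an unflagged imbalance.
- **That the 0.06 to 0.17 SD shift applies to Aim 1.** Aim 1 tests the effect of condition on change over four waves, and the baseline level is modelled as the intercept. A covariate biases the slope through its correlation with change, about which the documents say nothing. The intercept is not a complete answer either. The plan does not say that the condition effect on slope is conditional on it. If the baseline outcome were itself flagged, the rule would enter it into a model that already holds it as the first wave.
- **That a spurious covariate is likely and harmful.** The 40% and 64% need independent tests, whereas behavioural scales and diagnoses overlap. Flagged demographics are often in the model already. One needless covariate costs little: at a 0.33 SD imbalance its correlation with arm is about 0.16, variance inflation about 1.03, and the standard error rises about 1.4%.

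It can also be said that at rotation sites a check for imbalance is reasonable, because differences there may be systematic rather than due to chance. That is fair, but at this sample size the test is a weak screen. It argues for adjusting for named variables regardless of the p-value, with the observed-imbalance check kept as a supplement.

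**Conclusion.** The concern holds, in limited scope. For variables outside the fixed list, adjustment rests on a test unrelated to prognosis, and imbalances just short of 0.33 SD, or about 13 to 16.5 points for the projected rates considered, are left in. The consequence can be sized for Aim 2, at 0.06 to 0.17 SD for an unflagged imbalance of 0.20 to 0.33 SD. The top of that range needs an imbalance at the threshold and r = 0.5. For Aim 1 it cannot be sized from the documents.

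The costs are lost power, bias in trials with an unflagged imbalance, and discretion left to the analyst. The level of 0.05, the values of r, the 0.5 SD effect and the number of tests are assumptions. The relevant r is the one that remains after the fixed covariates, so the shifts may be smaller. Therapist clustering and urn balancing are not in the calculations; the urn makes a large substance-use imbalance less likely where it is applied.

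**What to change.** 1. Remove test-driven covariate selection from the main analyses.
2. Keep the whole fixed list from the Aims 1 & 3 section, including family income and caregiver education.
3. Add baseline substance use to the Aim 2 models.
4. Name in advance a few prognostic baseline variables that are already collected. Candidates for all models are prior ADHD medication and comorbid conduct or mood disorder. Baseline ADHD severity belongs in the Aim 2 models and in models for outcomes where it is not itself the first repeated measure; elsewhere it would enter as a covariate for its own trajectory.
5. Report baseline differences descriptively, without tests that drive the model.
6. Keep adjustment for observed imbalances as a labelled sensitivity analysis, which retains a check for the rotation sites.

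The cost is a short SAP revision, agreement on the named variables before outcome data are seen, and a few degrees of freedom if some prove unhelpful.
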